### 7.1.4 Biological characteristics

#### Population ITT

The following characteristics at inclusion will be described:

- Wafers (x10 /mm^3)
- PNN (/mm^3),
- Creatinine (μmol/L)
- Albumin (g/L)
- P rate (%)
- Hemoglobin (g/dL),
- Total bilirubin (Number of x normal)
- Conjugated bilirubin (number of x normal)
- AST (Number of x normal)
- ALAT (Number of x normal)
- PAL (Number of x normal)
- GGT (Number of x normal)
- AFP (Number of x normal)
- Blood glucose (g/L)
- V factor (%)
- Sodium (g/L)

### 7.1.5 Disease-related characteristics

#### Population ITT

The following characteristics at inclusion will be described:

- Tumor volume as % of liver volume ( $> 50\% vs \leq 50\%$ )
- Tumor extension (unilobar vs. bilobar)
- Number of nodules (1 vs 2-3 vs  $> 3$  vs infiltrating)
- Size of largest nodule in right and left livers (in mm)
- Presence of tumor portal thrombosis (No vs. Yes), and if so, type (Sectoral vs. Segmental vs. Sub-segmental)

## 7.2 Follow-up features

#### Population ITT

### 7.2.1 Definition of median follow-up time

Median follow-up time is defined as the time interval between the date of inclusion and the date of last news (patients alive or lost to follow-up) or, for deceased patients, the date of death (whatever the cause).

### 7.2.2 Evaluation of median follow-up time

The median follow-up time (for living patients) and its 95% confidence interval will be calculated in months. It will be estimated using the inverse Kaplan Meier method.

## 7.3 Evaluation of primary endpoint efficacy

#### Population CP

### 7.3.1 Definition of primary efficacy endpoint

The primary endpoint is the objective response rate 6 months after inclusion. Objective response (complete and partial response) is defined according to mRECIST criteria and based on centralized review (or on the investigator's opinion if review is not possible).

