Objectives	
Principal: Objective response rate (complete and partial response) according to mRECIST at 6 months assessed in centralized review
 
Secondary: Objective response rate (mRECIST) at 6 months assessed by the investigator Objective response rate at 6 months according to EASL criteria Time to treatment failure Best response according to mRECIST criteria Progression-free survival Overall survival Tolerance of the treatment Quality of life

Inclusion criteria	
 - Histologically proven HCC or according to EASL/Barcelona criteria for nodules ≥ 1 cm - Tumor not amenable to curative treatment (liver transplantation, surgical resection or percutaneous destruction) - Measurable targets according to mRECIST v1.1 criteria

	
 - Preserved liver function (in case of cirrhosis, Child-Pugh A or B7 without history of edemato-ascitic decompensation) - Tumor classified as BCLC A or B without portal or extrahepatic invasion or C if WHO = 1 - No prior treatment with chemotherapy, radiotherapy or transarterial embolization (with or without chemotherapy) - Age \geq 18 years - WHO 0 or 1 - Biological workup: platelets \geq 50,000/mm³, PNN \geq 1,000/mm³, creatinine level \leq 150 μmol/L - No heart failure (isotopic or echographic LVEF $>$ 50%) - Signed informed consent

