CAT scan for extra-hepatic evaluation	X		X (in case of contraindication to MRI)	X	X (thoracic every 6 months)	X (thoracic)
Portal Doppler if thrombosis is suspected on imaging	X	X (recommended)				
ECG	X					
Evaluation of left FEV	X					
BIOLOGICAL ASSESSMENT						
Biological check-up	X*	X**			X (liver test)	X (liver test)
AFP marker	X				X	X
Serology (HBsAg, anti-HBs, anti-HCV)	X					
Pregnancy test (within 7 days of inclusion)	X					
BIOLOGICAL STUDY						
Samples: 2 EDTA tubes of blood then centrifugation for aliquoting of 4 cryotubes of plasma and freezing at -20°C then -80°C		X (D0, D1, D2 and D3 of 1 ^{ière} HEC)				
IMAGERY*** : CT cone beam or CT scan without injection during the procedure						

* Complete biological check-up: CBC/platelets, PT, AST, ALT, alkaline phosphatases, GGT, bilirubin (total, free and conjugated), factor V, blood ionogram, creatinine, albumin, blood sugar, blood calcium

** Biological check-up before each HEC: CBC, platelets, blood ionogram, creatinine, albumin, ASAT, ALAT, PAL, GGT, total and conjugated bilirubin, PT

*** : An anonymized copy of the imaging is to be sent to the FFCD for centralized review

**** : hepatic MRI (or CT) / ultrasound of the liver by a trained operator alternating every 3 months for 2 years

I. OBJECTIVES OF THE TRIAL

I.1 Main objective

The objective of this non-randomized phase II study is to evaluate the objective response rate (complete and partial response) at 6 months, assessed according to the mRECIST criteria in centralized review.

I.2 Secondary objectives

The secondary objectives of this study are to evaluate:

- The investigator-assessed 6-month objective response rate (mRECIST)
- Time to treatment failure
- The best answer according to mRECIST
- Objective response rate at 6 months (EASL)
- Progression-free survival
- Overall survival
- Tolerance of the treatment
- Quality of life (QLQ-C30 questionnaires and its HCC18 module specific to HCC)

II. PATIENT SELECTION

II.1 Inclusion criteria

- Histologically proven HCC or according to EASL/Barcelona criteria for nodules ≥ 1 cm
- Tumor not amenable to curative treatment (liver transplantation, surgical resection or percutaneous destruction)
- Measurable targets according to mRECIST v1.1 criteria
- Preserved liver function (in case of cirrhosis, Child-Pugh A or B7 without history of edemato-ascitic decompensation)
- Tumor classified as BCLC A or B without portal or extrahepatic invasion or C if WHO= 1

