Note: The time between collection and freezing (at -20°C) of plasma should not exceed 1 hour.

Complete the sample census form (present in the study investigator's binder) and send it by [contact]) or by email ([contact]) to the FFCD as soon as the 4 sampling times have been completed.

The repatriation of the samples to the CRB (biological resource center) EPIGENETEC of the FFCD, will be done at the end of the study by a specialized carrier.

Imaging for correlation with VEGF assay

Perform a cone beam CT or CT scan without injection after the 1^{ière} HEC.

An anonymized copy should be sent to the FFCD. A blank CD ROM is provided in the patient's CRF.

X. CENTRALIZED READING OF MRI AND CT

Responses will be evaluated according to the mRECIST version 1.1 (primary endpoint) and EASL (secondary endpoint) criteria (Appendices 4 and 5) and will be reviewed by a panel of independent radiologists who will confirm responses and dates of tumor progression or recurrence once all study examinations have been retrieved.

For this purpose, an **anonymized copy on CD ROM** (present in each observation book) **of each morphological evaluation until progression** (even if beyond 6 months) (MRI) is to be made. **The copies will be sent to the CRGA of the FFCD for centralized review.**

XI. MANAGEMENT OF SERIOUS ADVERSE EVENTS (SIA)

1. Security assessment parameters

Safety will be assessed by evaluating the general and clinical condition of patients and by collecting events occurring between visits during consultations. Toxicities will be assessed using the NCI-CTC-AE version 4.0 toxicity scale (see Appendix 6).

In case of an emergency, the patient, his family or his physician should call the investigator to warn of an event.

2. Definitions

a. Adverse Event (AE)

An adverse event is a harmful occurrence in a person who is a subject of biomedical research, whether or not the occurrence is related to the research or the product being investigated.

All adverse events will be recorded in the observation book on the pages provided.

b. Serious Adverse Event (SAE)

A serious adverse event (SAE) is considered to be any event:

- Resulting in death,
- Life-threatening,
- Leading to hospitalization or prolonged hospitalization,
- Causing permanent disability or severe temporary incapacity,
- Causing a birth defect, fetal malformation or abortion,
- Medically significant.

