If it is a serious unexpected adverse reaction, or if it is a new fact, the sponsor writes an initial report which will be transmitted to the ANSM, the CPP and the EMA (via EudraVigilance) within 7 days in case of death, otherwise within 15 days.

If it is an expected serious adverse event, it will be collected for the semi-annual and annual safety reports.

4. Modalities and duration of follow-up of individuals following the occurrence of adverse events.

The investigator is responsible for appropriate medical follow-up of patients until resolution or stabilization of the effect or until the patient's death. This may sometimes mean that this follow-up extends beyond the patient's discharge from the trial.

He/she transmits the additional information to the sponsor using an SAE reporting form (checking the Follow-up No. X box to specify that it is a follow-up report and not an initial report) within 24 hours of obtaining it. It also forwards the last follow-up to the resolution or stabilization of the SAE.

He keeps the documents concerning the suspected adverse reaction in order to allow, if necessary, to complete the information previously transmitted.

It responds to requests for additional information to document the initial observation.

XII. STATISTICAL ANALYSIS

XII.1 Provisional timetable for the study

With an expected rate of one patient per month per center, i.e. 10 patients per month, and with a suspension of inclusions between stage 1 and 2, the study schedule will be as follows:

Stage 1: 43 evaluable patients

- Expected start date of inclusion (stage 1): September 2014
- Anticipated end date of inclusion stage 1: February 2015
- Judging criterion at 6 months: August 2015
- Stage 1 analysis (+ 6 months): February 2016

Stage 2: 43 evaluable patients

- Expected start date of inclusion: February 2016
- Expected completion date of inclusion stage 2: July 2016
- Judging criterion at 6 months: January 2017
- Final analysis of primary endpoint (+ 6 months): July 2017
- 2-year overall survival analysis: January 2020

XII.2 Judging criteria

XII.2.1 Main criterion

The primary endpoint is the rate of patients with objective response (complete response or partial response) **at 6 months after inclusion** according to mRECIST criteria and centralized review.

XII.2.2 Secondary Criteria

The secondary endpoints of this study are:

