If 29 or more patients have an objective response, the treatment is declared effective (rejection of H0)

Taking into account a 5% rate of patients lost to follow-up or not evaluable, **91 patients** will be included. The decision rules will be adapted based on the number of evaluable patients actually included.

XII.4 Statistical analysis plan

A statistical analysis plan will be written prior to freezing the database.

Analysis Populations:

The characteristics of the patients included in the study will be described in strict intention-to-treat (ITT). Efficacy analyses will be performed on a modified intention-to-treat (mITT) basis: all evaluable patients included in the study regardless of eligibility criteria. A patient is considered evaluable if he/she has had at least one chemoembolization and one post-treatment evaluation.

Population evaluable for safety:

The ITT population that received at least one chemoembolization.

Statistical analysis:

The description of the variables will be done using percentages (95% confidence interval) for qualitative variables and using mean (standard deviation) and median (Min-Max) as well as the inter-quartile range (Q1-Q3) for quantitative variables.

The estimation of censored data will be done by the Kaplan Meier (KM) method. Times will be described by medians and rates at different time points with their 95% confidence intervals. The median follow-up time will be calculated using the reverse Kaplan Meir method.

XII.5 Independent Committee

An independent committee composed of 1 clinician / 1 methodologist-statistician / 1 pharmacovigilant expert / 1 radiologist will be set up before the beginning of the trial. It will meet regularly during the course of the study according to the rate of inclusion.

It will have to rule on the declared ADRs. It can also be seized at any time by the Sponsor in case of significant facts on the tolerance (ADRs and AEs) of the treatment.

XIII. JUSTIFICATION OF THE TEST

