### **3 Introduction**

#### **3.1 Objectives of the trial**

##### **3.1.1 Objective main**

The primary objective of the study is to evaluate the objective response rate (complete and partial response) at 6 months, assessed according to mRECIST criteria in centralized review.

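### SAP 7.3.1 adds an investigator fallback to the centrally reviewed primary endpoint, with no defined trigger, no count of its use and no central-only analysis

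*SAP*

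**What the plan says.** The protocol gives the same definition in three places. The synopsis objective is response "according to mRECIST at 6 months assessed in centralized review". Section I.1 has it "assessed according to the mRECIST criteria in centralized review". Section XII.2.1, which defines the endpoint, has it "according to mRECIST criteria and centralized review". SAP 3.1.1 repeats this: "assessed according to mRECIST criteria in centralized review". Protocol section X states that responses "will be reviewed by a panel of independent radiologists who will confirm responses". It names no alternative reader.

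SAP 7.3.1 differs. Response is "based on centralized review (or on the investigator's opinion if review is not possible").

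Evaluability does not depend on a central reading. Protocol XII.4 states: "A patient is considered evaluable if he/she has had at least one chemoembolization and one post-treatment evaluation". SAP 5.1.2 has the same rule and adds rules for patients with no imaging, for death within 6 months and for a missing 6-month assessment. It has none for a scan that exists but was not read centrally. The only listing it requires is of patients excluded from the primary-endpoint population.

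SAP 7.3.2 plans one rate with a one-sided exact 95% interval. The other 6-month response analyses are mRECIST by the investigator (SAP 7.4.1) and EASL by central review and by the investigator (SAP 7.4.2). SAP 4.6.1 reports that 22 of 44 evaluable patients responded, that 19 were needed, and that the trial stopped for efficacy.

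**The concern.** The trial is open-label with a single arm, and the independent panel is there to confirm responses. A response that enters the primary rate on the investigator's opinion alone has not had that confirmation. Because the trigger is open, the choice of which readings count could be made case by case, by people who already know the investigator's result.

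The separate investigator mRECIST rate and the central EASL rate limit how far a reader effect could stay hidden. Neither shows how many primary-endpoint results came from the fallback, and neither gives the central mRECIST rate on its own. From these documents a reader cannot tell whether the 22/44 behind the efficacy stop is the protocol's endpoint or a mixture. SAP 4.6.1 does not say whether the fallback was applied at the interim. The margin over the bound was 22 − 19 = 3 responders, so the number of fallback responses is needed to judge how firm the stop is.

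**Working it through.** **Inputs.** Null rate 25%, hoped-for rate 40%, one-sided alpha 5%, power 90%, bounds of 18/43 and 29/86 for efficacy and 10/43 for futility (protocol XII.3). Interim bound 19/44 and result 22/44 (SAP 4.6.1). The number of fallback responders, k, is not in the documents; it is varied below as an assumption.

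**The plan's own figures.** With the stated bounds, the exact two-stage binomial calculation gives a type I error of 0.0474 and a power of 0.9023. 86/0.95 = 90.5, which rounds up to 91. The design reproduces.

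**Adapted bound.** Protocol XII.3 says "The decision rules will be adapted based on the number of evaluable patients actually included" but gives no formula. I assume Fleming's form with total N = 86:

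bound(n) = round(0.25n + 1.645 × √(86 × 0.25 × 0.75)) + 1, where 1.645 × √16.125 = 6.61.

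- n = 43: 10.75 + 6.61 = 17.36, bound 18
- n = 44: 11 + 6.61 = 17.61, bound 19
- n = 86: 21.5 + 6.61 = 28.11, bound 29

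All three match the documents. Rounding down instead of to the nearest integer would give 18 at n = 44, not the 19 that the SAP applied, so nearest-integer rounding is used.

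**Lower limits.** For x responders of n, the one-sided 95% Clopper-Pearson limit is the 5% quantile of Beta(x, n − x + 1). The tail is P(X ≥ x) at a response rate of 25%.

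**(a) Investigator-only responders counted as failures, n = 44, bound 19**

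| k | Result | Lower limit | Tail at 25% | Bound met |
|---|---|---|---|---|
| 0 | 22/44 | 36.8% | 0.0003 | yes |
| 1 | 21/44 | 34.6% | 0.0009 | yes |
| 2 | 20/44 | 32.5% | 0.0025 | yes |
| 3 | 19/44 | 30.4% | 0.0064 | yes |
| 4 | 18/44 | 28.4% | 0.0148 | no |
| 5 | 17/44 | 26.3% | 0.0318 | no |
| 6 | 16/44 | 24.3% | 0.0626 | no |

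The bound is missed at 4/22 = 18% of responses. The 25% rate is no longer excluded at 6/22 = 27%.

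**(b) The same responders removed from numerator and denominator, adapted bound**

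| k | Result | Bound | Lower limit | Tail at 25% | Bound met |
|---|---|---|---|---|---|
| 4 | 18/40 | 18 | 31.5% | 0.0047 | yes |
| 5 | 17/39 | 17 | 30.0% | 0.0086 | yes |
| 6 | 16/38 | 17 | 28.5% | 0.0156 | no |
| 8 | 14/36 | 17 | 25.3% | 0.0461 | no |
| 9 | 13/35 | 16 | 23.6% | 0.0756 | no |

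**(c) Fallback readings half responders, half non-responders (assumption), all excluded.** Removing 8 patients leaves 18/36: bound 17, met, lower limit 35.3%. Removing 14 leaves 15/30: bound 15, still met, lower limit 33.9%.

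**The case against.** The strongest reply is that this is an operational rule of the kind a SAP is meant to supply. Protocol XII.4 foresees a SAP before database freeze, objective statements do not normally carry rules for missing readings, and 7.3.1 keeps central review as the rule. Without the fallback, SAP 6.4 (missing data not replaced) and 6.6 (missing values left out of percentages) would drop unread patients from the denominator. Counting them as failures has no basis in the documents, and the break point of 4 comes from that version. Under exclusion the stop is sturdier, and if fallback readings respond at the observed 50% it survives the loss of 14 of 44 patients. At that share, 4 investigator-only responses would imply about 8 of 44 scans (18%) without a central reading, which nothing in the documents suggests. The separate investigator and EASL rates would also show reader disagreement.

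Most of this stands, and it bears on weight. Some rule for unread scans is needed, counting them as failures is a deliberately conservative choice, and the stop may well be unaffected. What remains is that the added rule changes who assesses the primary endpoint in an open-label trial, that protocol XII.2.1 does not contain it, and that no planned output would show how often it was used. The ordinary reading of the trigger (images missing or unreadable) is sensible, but it is not written down.

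**Conclusion.** The concern holds and should be fixed. The SAP's primary-endpoint definition departs from the protocol's and from SAP 3.1.1. In the text available, the trigger is undefined, its use is uncounted and no central-only mRECIST rate is planned.

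Its effect on the result is conditional. The efficacy decision is sensitive only if at least 4 of the 22 responses were investigator-only and are counted as failures, or at least 6 if they are excluded and the bound is adapted. The 25% rate stays excluded up to 5 and up to 8 such responses respectively. The exclusion figures for the bound rest on the assumed Fleming formula, and every scenario rests on an assumed number of fallback cases, which may be zero. The documents do not show that the efficacy conclusion is wrong; they do not let a reader confirm that it rests on the protocol's endpoint.

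**What to change.** 1. Reconcile SAP 7.3.1 with protocol XII.2.1, and state that the fallback is an addition to the protocol definition.
2. Limit the trigger to stated cases: images not received, or images judged unreadable by the panel.
3. Report how many of the 44 assessments, and how many of the 22 responses, used the fallback, with reasons.
4. Add a central-reading-only sensitivity analysis of the rate, its one-sided exact interval and the stopping rule, in two versions: (i) unread patients counted as non-responders, labelled as conservative and not an existing protocol rule; (ii) unread patients excluded, with the bound adapted to n.
5. In both versions apply SAP 5.1.2 first. Deaths within 6 months stay failures, later non-responses stay non-responses, and a late response without 6-month imaging goes to the review that section requires. None of these is treated as simply unread.

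The cost is SAP wording and one extra table, since protocol sections VII.2 and X already require images to be sent for central review. The drawback is a second, possibly slightly lower, rate to explain beside the primary one. Version (ii) shows how much of any drop comes only from counting unread scans as failures. If the fallback count is zero, one sentence saying so settles the point.

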### 7.3.2 Evaluation of primary efficacy endpoint

The objective response rate at 6 months will be calculated and presented with its one-sided 95% confidence interval (exact confidence interval, binomial distribution).

## 7.4 Evaluation of secondary efficacy endpoints

### 7.4.1 OR patient rate by investigator and mRECIST

#### 7.4.1.1 Definition

The rate of patients in objective response (complete and partial response) 6 months after inclusion according to mRECIST criteria will also be evaluated according to the investigator.

#### **7.4.1.2 Evaluation**

The objective response rate at 6 months will be calculated and presented with its 95% confidence interval.

### **7.4.2 OR patient rate according to EASL**

#### **7.4.2.1 Definition**

The rate of objective response (complete and partial response) 6 months after inclusion will also be evaluated according to EASL criteria in centralized review and according to the investigator.

#### **7.4.2.2 Evaluation**

The objective response rate at 6 months will be calculated and presented with its 95% confidence interval.

### **7.4.3 Time to treatment failure**

#### **7.4.3.1 Definition**

It is defined as the time between the date of inclusion and the date of definitive cessation of treatment or death (whatever the cause). Patients without definitive treatment discontinuation and not deceased will be censored at the date of their last HEC.

